6.2.2. Definition of Baseline and Postbaseline Measures

Baseline

Period 1 (Weeks 0 to 52)

The baseline value for efficacy variables measured at scheduled visits is defined as the last nonmissing measurement on or prior to the date of first study drug administration in the originating study (expected at Week 0, Visit 2 of the originating study). For patients who directly enroll into Study JAHN without having completed an originating study, baseline value for efficacy variables measured at scheduled visits is defined as the last nonmissing measurement on or prior to the date of first study drug administration in Study JAHN.

The baseline value for the daily diary assessments is the mean of the nonmissing assessments in the 7 days prior to the date of first study drug administration in the originating study (expected at Week 0, Visit 2).

If there are <4 nonmissing assessments in the baseline diary window, the interval lower bound can be extended up to 7 additional days, one day at a time, to obtain the most recent 4 nonmissing values. If there are not at least 4 nonmissing assessments in the baseline period, the baseline mean is missing.

Additionally, the Study JAHN baseline may be derived for some efficacy analyses (eg, patients enrolled directly into Study JAHN without having completed an originating study). In this case, the Study JAHN baseline is defined as the last nonmissing measurement on or prior to the date of first study drug administration in Study JAHN. For daily diary data, the baseline is the mean of the nonmissing assessments in the 7 days prior to the date of first study drug administration in the JAHN study. If there are <4 nonmissing assessments in the baseline diary window, the interval lower bound can be extended up to 7 additional days.

For patients who are enrolled from an originating study and do not require washout, the baseline will be the last visit of the originating study. However, patients who received oral systemic AD treatment as rescue therapy during the originating study require additional time to complete the

required 4-week washout and have an additional screening visit in Study JAHN (Visit 1 [Week 0]). Thus, for these patients the last nonmissing measurement on or after last visit of originating study and on or prior to first dose of study drug in Study JAHN will serve as the baseline.

For patients who do not require washout, baseline will be the last visit of the originating study. Patients who received oral systemic AD treatment as rescue therapy during the originating study require a 4-week washout and will have an additional screening visit in Study JAHN (Visit 1 [Week 0]). The assessments collected at this visit will provide the Study JAHN baseline for these patients. If labs were not collected at this visit, then the most recent lab value collected at the last visit of the originating study will be used as baseline.

Period 2

For analysis of endpoints assessed at scheduled visits in Period 2, baseline from originating study will be used for categorical endpoints, such as EASI75, Itch NRS ≥ 4 -point improvement response, etc. Baseline from originating study will also be used for EASI-related, continuous endpoints, such as EASI change or percent change from baseline. For the other continuous endpoints such as Itch NRS and DLQI change from baseline, the analysis will be done using the Week 52 baseline. The methodology for defining Week 52 as the baseline is the same as the methodology for defining Week 0 of the originating study described above, anchoring on the first study drug administration of Period 2.

Safety Analyses

Safety analyses for treatment Period 1, and for Treatment Periods 1 and 2 combined (box plots of laboratory analytes and vital signs) will be conducted using the Study JAHN baseline, which is defined as the last nonmissing scheduled (planned) measurement on or prior to the date of first study drug administration for continuous measures by-visit analyses and non-missing measurements on or prior to the date of first study drug administration in Study JAHN for all other analyses. Safety analyses for Treatment Period 2 will be conducted for AEs only. Baseline for Treatment Period 2 is defined as nonmissing measurements on or prior to the date of first study drug administration in Treatment Period 2 of Study JAHN.

Postbaseline

Period 1(Weeks 0 to 52)

Nonmissing postbaseline efficacy data collected at scheduled visits will be used for analyses. If an assessment is missing at a scheduled visit, an unscheduled postbaseline assessment can be used provided it falls within a ± 4 -day window of the scheduled visit date. If there is more than 1 unscheduled visit within the defined visit window and no scheduled visit assessment is available, the unscheduled visit closest to the scheduled visit date will be used. If 2 unscheduled visits of equal distance are available, then the latter of the 2 will be used. If there is no nonmissing measure collected at the scheduled visit or an unscheduled visit falling within the visit window, the assessment is missing for that scheduled visit.

Diary endpoints were collected up to Week 16 in Period 1 of Study JAHN. Postbaseline daily diary endpoints will be the mean of weekly visit windows (diary windows) anchored on day of first dose (Day 1) for Weeks 1 through 14 as follows:

Week	Days
1	1-7
2	8-14
3	15-21
4	22-28
5	29-35
6	36-42
7	43-49
8	50-56
9	57-63
10	64-70
11	71-77
12	78-84
13	85-91
14	92-98

Week 16 Daily Diary Window Construction

The following sequential steps will be used to determine the Week 16 diary window. The general goal is to anchor on the scheduled Week 16 visit (or a proximal unscheduled visit) if such a visit exists or to use an interval based on days in study for cases where a scheduled Week 16 or a proximal surrogate does not exist.

Step 1: If the Week 16 scheduled visit exists, the Week 16 diary interval is the 7 days prior to the Week 16 date provided that window has at least 4 nonmissing observations. If there are <4 nonmissing observations, the diary window's lower bound will be extended 1 day at a time (up to Day 99) to a maximum of 14 days prior to the Week 16 date until 4 nonmissing observations are obtained. If after extending this diary window's lower bound to 14 days there are <4 nonmissing observations, then go to Step 2.

Step 2: If the Week 16 scheduled visit does not exist, the 7 days prior to the last visit (scheduled or unscheduled) occurring after Day 105 and on or before a scheduled visit occurring after Week 16 will constitute the Week 16 diary window provided that window contains at least 4 nonmissing observations. If there are <4 nonmissing observations, the diary window's lower

bound will be extended 1 day at a time (up to Day 99) to a maximum of 14 days prior to the unscheduled visit date until 4 nonmissing observations are obtained. If after extending this diary window's lower bound to 14 days there are less than 4 nonmissing observations then go to Step 3.

Step 3: If neither a Week 16 scheduled visit or an unscheduled visit to act as a surrogate for the Week 16 diary window is available, then the Week 16 window will be Day 106 to Day 112. If there are <4 nonmissing observations, the diary window's lower bound will be extended 1 day at a time to Day 99 until 4 nonmissing observations are obtained.

If the steps above do not detect a window with at least 4 nonmissing observations, then the Week 16 window is 7 days from either the Week 16 visit, the surrogate visit, or Day 106 through 112, and the mean is missing and subject to imputation rules.

Week 15 Daily Diary Window Construction

The lower boundary of the Week 15 diary window is defined as Day 99. The upper bound of the Week 15 diary window is the minimum of either Day 105 or the lower bound of the Week 16 diary window -1. Consequently, Week 15 may be <4 days if the Week 16 scheduled visit is before Day 112. Moreover, as the Week 15 diary window cannot exceed 7 days, there could be daily assessments between the Weeks 15 and 16 diary windows that do not fall into a diary window. If after constructing the diary windows there are fewer than 4 nonmissing values, the mean for Week 15 is missing and subject to imputation rules.

PostBaseline

Period 2 (Study Weeks 52-68)

Diary endpoints were collected up to Week 16 in Period 2 of JAHN. For Treatment Period 2, postbaseline daily diary endpoints will be the mean of weekly visit windows (diary windows) anchored on day of the Week 52 visit for Weeks 53 through 66 as follows:

Week of Period 2	Days in Period 2
53	1-7
54	8-14
55	15-21
56	22-28
57	29-35
58	36-42
59	43-49
60	50-56
61	57-63

62	64-70
63	71-77
64	78-84
65	85-91
66	92-98

Week 68 Daily Diary Window Construction

Week 68 daily diary window construction for Period 2 will follow the exact same steps as the window construction for Week 16 in Period 1.

Week 67 Daily Diary Window Construction

Week 67 daily diary window construction for Period 2 will follow the exact same steps as the window construction for Week 15 in Period 1.

Handling of Duplicate Diary Records

If there is more than 1 diary record on a particular date, the first record on that particular date will be used in the analysis.

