**Figure JAHN.1. Illustration of study design for Clinical Protocol I4V-MC-JAHN.**

#### 4.3.1.1. Screening Period

The duration of the screening period for patients enrolled in JAHN(7) is between 8 and 35 days prior to Visit 1 (Week 0). At Visit 0, the patient will sign the informed consent form (ICF) prior to any study assessments, examinations, or procedures being performed. All screening procedures will be performed according to the Schedule of Activities ([Attachment 1](#)).

Patients who receive a purified protein derivative (PPD) skin test at Visit 0 will need to return within 48 to 72 hours later to read the skin test. Prior to enrollment, treatments for AD will be washed out: 4 weeks for systemic treatments and 2 weeks for topical treatments (not including emollients). Patients will be required to use emollients daily during the 14 days preceding enrollment and throughout the study. If patients have been using emollients daily at the time of screening, then those cumulative days can be utilized to meet inclusion criterion [8]. Additionally, collection of data through daily diaries will be required throughout the screening period. The baseline for the daily electronic patient reported outcome (ePRO) will be the average score of the 7 days prior to enrollment; thus, the minimum screening window was set at 8 days.

All patients who have not previously received the herpes zoster vaccine by screening will be encouraged (per local guidelines) to do so prior to enrollment. Refer to the exclusion criterion [26] for additional information regarding herpes zoster vaccination.

Patients who meet all of the inclusion and none of the exclusion criteria for this addendum (Section 4.5) will continue to Visit 1 and follow all study procedures described in the Schedule of Activities ([Attachment 1](#)) and Section 9 of the main protocol.

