6.12. Health Outcomes/Quality-of-Life Analyses

The general methods used to summarize health outcomes and quality-of-life measures, including the definition of baseline value for assessments, are described in Section 6.2.

Health outcomes and quality-of-life measures will generally be analyzed according to the formats discussed in Section 6.2.

Table JAHN.6.6 includes the descriptions and derivations of the health outcomes and quality-of-life measures.

Table JAHN.6.7 provides the detailed analyses including analysis type, method and imputation, population, time point, and comparisons for health outcomes and quality-of-life measures.

Table JAHN.6.6. Description and Derivation of Health Outcomes and Quality-of-Life Measures

Measure	Description	Variable	Derivation / Comment	Imputation Approach if Missing Components
Itch Numeric Rating Scale (NRS)	The Itch Numeric Rating Scale (NRS) is a patient-administered, 11-point horizontal scale anchored at 0 and 10, with 0 representing “no itch” and 10 representing “worst itch imaginable.” Overall severity of a patient’s itching is indicated by selecting the number that best describes the worst level of itching in the past 24 hours (Naegeli et al. 2015; Kimball et al. 2016). Refer to Section 6.2.2 for details on how to calculate the weekly score which will be used in the continuous analysis.	
 ▪ Itch NRS score 	Single item. Range 0-10. Refer to Section 6.2.2 on how to derive the weekly score.	Refer to Section 6.2.2 on how to derive the weekly score.
		
 ▪ Change from baseline in Itch NRS ▪ Percent change from baseline in Itch NRS 	Change from baseline: observed Itch score – baseline Itch score % change from baseline: $100 \times \frac{\text{Observed score} - \text{Baseline}}{\text{Baseline}}$	Missing if baseline or observed value is missing.
		
 ▪ 4-point Itch improvement in subgroup of patients with baseline Itch NRS ≥ 4 	Change from baseline ≤ -4 and baseline ≥ 4	Missing if baseline is missing or <4 or observed value is missing.

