Skin Pain Numeric Rating Scale (NRS)	Skin Pain NRS is a patient-administered, 11-point horizontal scale anchored at 0 and 10, with 0 representing “no pain” and 10 representing “worst pain imaginable.” Overall severity of a patient’s skin pain is indicated by selecting the number that best describes the worst level of skin pain in the past 24 hours. Refer to Section 6.2.2 for details on how to calculate the weekly score which will be used in the continuous analysis.	
 ▪ Skin Pain NRS score 	Single item; range 0-10. Refer to Section 6.2.2 on how to derive the weekly score.	Refer to Section 6.2.2 on how to derive the weekly score.
		
 ▪ Change from baseline in Skin Pain NRS 	Change from baseline: observed skin pain score – baseline skin pain score	Missing if baseline or observed value is missing.

Measure	Description	Variable	Derivation / Comment	Imputation Approach if Missing Components
Atopic Dermatitis Sleep Scale (ADSS)	The Atopic Dermatitis Sleep Scale (ADSS) is a 3-item, patient-administered questionnaire developed to assess the impact of itch on sleep including difficulty falling asleep, frequency of waking, and difficulty getting back to sleep last night. Patients rate their difficulty falling asleep and difficulty getting back to sleep, items 1 and 3, respectively, using a 5-point Likert-type scale with response options ranging from 0 “not at all” to 4 “very difficult.” Patients report their frequency of waking last night, item 2, by selecting the number of times they woke up each night, ranging from 0-29 times. The ADSS is designed to be completed each day with respondents thinking about sleep “last night.” Each item is scored individually. Refer to Section 6.2.2 for details on how to calculate the weekly score which will be used in the continuous analysis.	
 ▪ Item 1 score of ADSS ▪ Item 2 score of ADSS ▪ Item 3 score of ADSS 	Single items: Item 1, range 0-4; Item 2, range 0-29; Item 3, range 0-4. Refer to Section 6.2.2 on how to derive the weekly score.	Refer to Section 6.2.2 on how to derive the weekly score.
		
 ▪ Change from baseline in score of Item 1 of ADSS ▪ Change from baseline in score of Item 2 of ADSS ▪ Change from baseline in score of Item 3 of ADSS 	Change from baseline: observed ADSS item score – baseline ADSS item score	Missing if baseline or observed value is missing.

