
To estimate the effect of starting baricitinib 2-mg on clinical measures and patient-reported outcomes.
	
 • Proportion of patients with a 4-point improvement from baseline in Itch NRS at Weeks 1 and 4 • Proportion of patients achieving EASI90 at Weeks 4, 16, 24 and 52 • Percent change from baseline in EASI score at Weeks 4, 16, 24, and 52 • Proportion of patients achieving EASI50 at Weeks 4, 16, 24, and 52 • Proportion of patients achieving SCORAD75 at Weeks 4, 16, 24, and 52 • Mean change from baseline in SCORAD at Weeks 4, 16, 24, and 52 • Proportion of patients achieving SCORAD90 at Weeks 4, 16, 24, and 52 • Mean change from baseline in Skin Pain NRS at Weeks 1, 4, and 16 • Mean change from baseline in the score of the items of the ADSS at Weeks 1, 4, and 16 • Mean change from baseline in BSA affected at Weeks 4, 16, 24, and 52 • Percent change from baseline in Itch NRS at Weeks 1, 4 and 16 • Mean change from baseline in the total score of the POEM at Weeks 4, 16, 24, 52 • Mean change from baseline in the PGI-S-AD scores at Weeks 1, 4, and 16 • Mean change from baseline in the HADS at Weeks 4, 16, 24, and 52 • Mean change from baseline in the DLQI scores at Weeks 4, 16, 24, and 52 • Mean change from baseline in the WPAI-AD components (absenteeism, presenteeism, work productivity loss, and activity impairment) at Weeks 4, 16, 24, and 52 • Mean change from baseline in the EQ-5D-5L scores at Weeks 4, 16, 24, and 52

Abbreviations: ADSS = Atopic Dermatitis Sleep Scale; BSA = body surface area; DLQI = Dermatology Life Quality Index; EASI = Eczema Area and Severity Index; EQ-5D-5L = European Quality of Life–5 Dimensions–5 Levels; HADS = Hospital Anxiety Depression Scale; NRS = Numeric Rating Scale; PGI-S-AD = Patient Global Impression of Severity–Atopic Dermatitis; POEM = Patient-Oriented Eczema Measure; SCORAD = SCORing Atopic Dermatitis; WPAI-AD = Work Productivity and Activity Impairment-Atopic Dermatitis.

APP.1.2. Study Design

APP.1.2.1 Summary of Study Design

[figure not shown]
Study JAHN(7.1) is a Phase 3, multicenter, open-label study to evaluate the effects of starting baricitinib 2-mg in patients with atopic dermatitis (AD). The study will consist of 4 study periods and 1 substudy: randomized treatment withdrawal and downtitration. Unlike the main protocol, patients do not have to complete an originating study.

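### The Week 1 diary window includes the day of first dose, so a pre-dose ADSS entry is averaged into the first on-drug week; Week 53 and its baseline use different anchors

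*SAP*

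**What the plan says.** **Period 1 windows.** SAP Section 6.2.2 makes each weekly diary score a mean over a window "anchored on day of first dose (Day 1) for Weeks 1 through 14 as follows". The table there gives Week 1 as Days 1 to 7, Week 2 as Days 8 to 14, and so on to Week 14 as Days 92 to 98.

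**Baseline.** For patients who enrol directly, the same section takes the diary baseline as "the mean of the nonmissing assessments in the 7 days prior to the date of first study drug administration in the JAHN study". SAP Appendix 1 (APP.1.2.3.2.2) uses the same anchor. Protocol Section 4.3.1.1 says the daily baseline "will be the average score of the 7 days prior to enrollment". Neither definition includes the dosing day. If a date has two diary records, the SAP keeps the first.

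**Recall periods (SAP Table JAHN.6.6).** For sleep: "The ADSS is designed to be completed each day with respondents thinking about sleep" during the night just past. The Itch NRS is answered by "selecting the number that best describes the worst level of itching in the past 24 hours". Skin Pain NRS also asks for the worst level over 24 hours, and PGI-S-AD asks about symptoms over 24 hours.

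**Period 2.** The diary windows are "anchored on day of the Week 52 visit for Weeks 53 through 66 as follows", with Week 53 as Days 1 to 7. The Week 52 baseline is built like the Week 0 baseline but "anchoring on the first study drug administration of Period 2".

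**Use.** The addendum's exploratory objectives (APP.1.1.3) name Week 1 for itch (4-point response and percent change), Skin Pain and PGI-S-AD, and for sleep: "Mean change from baseline in the score of the items of the ADSS at Weeks 1, 4, and 16". SAP Table JAHN.6.7 lists exploratory diary analyses for the substudy over Weeks 52 to 68.

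**The concern.** The dosing-day entry is classed as post-baseline, and no rule drops it or splits it by time of dose. For the ADSS it cannot reflect treatment, because it describes the night before the first tablet. For the 24-hour items it covers at least some hours before the dose, and for the two worst-level items a pre-dose peak can set the score. A value that is wholly or partly pre-treatment is therefore averaged into the first on-drug week, which pulls the estimated change towards zero at a named time point.

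In Period 2 the baseline and the first post-baseline week hang on two different dates. If those dates differ, the visit-day entry belongs to both windows, and Week 53 holds more entries from before the rerandomized treatment began. The early contrast between continued dose, lower dose and placebo is then diluted.

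**Working it through.** The documents give no figure for this, so there is nothing to reproduce beyond the window table. Week k = Days 7(k − 1) + 1 to 7k gives 1–7, 8–14 and 92–98 for Weeks 1, 2 and 14, as printed.

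**Week 1 mean change.** Let n be the number of nonmissing entries including Day 1, and s the share of the Day 1 rating that reflects pre-dose time. Assume that the pre-dose part equals baseline on average and that the effect is constant over Days 2 to 7. The weekly mean then recovers a fraction 1 − s/n of the on-drug change.

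- ADSS, s = 1 (follows from the recall period): n = 7 gives 6/7 = 0.857; n = 6 gives 0.833; n = 5 gives 0.80; n = 4 gives 0.75.
- 24-hour items, s unknown because the time of diary entry is not stated. With s = 1 (entry made before the tablet) the fractions are those above. With s = 0.5 (an illustration) they are 0.929 for n = 7 and 0.875 for n = 4.
- Section 6.2.2 states a minimum of four entries for baseline and for Weeks 15 and 16, but not for Weeks 1 to 14. As written, a week with Day 1 as its only entry (n = 1) could count, and for the ADSS the fraction is then 0.

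**Four-point itch response at Week 1 (addendum).** A patient whose Day 1 entry equals baseline needs a mean fall of 4 × 7/6 = 4.67 points on Days 2 to 7 to be scored a 4-point responder with a full diary. This is the s = 1 upper bound. To show what it could do to a response rate, assume that the Days 2–7 change is normal with SD 2 and mean m (not from the documents). The rates are Φ((−4 − m)/2) without Day 1 and Φ((−4.67 − m)/2) with it:

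- m = −1: 6.7% becomes 3.3%
- m = −2: 15.9% becomes 9.1%
- m = −3: 30.9% becomes 20.2%

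**Week 53.** Let L be the days from the Week 52 visit to the first Period 2 dose. The baseline is the 7 days before that dose, so L entries fall in both windows. Entries up to and including the dosing day number L + 1 of the 7 in Week 53. If none of them carries a treatment effect (s = 1), the fraction recovered is (6 − L)/7:

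- L = 0: 0.857, no overlap
- L = 1: 0.714, one shared entry
- L = 2: 0.571, two shared entries

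The documents do not give L. Protocol Section 4.6.4 says tablets are usually taken at the start of the day, so a first Period 2 dose on the day after the visit is plausible, but it is not stated.

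**The case against.** The strongest reply is that nothing important depends on this. The addendum is single-arm, descriptive and unpowered. Its primary endpoint is IGA at Week 16, its secondary itch endpoint is also at Week 16, and every named Week 1 diary endpoint is exploratory. Table APP.1.4 labels its 4-point itch row for Weeks 0 to 16 as secondary, but the secondary objective limits that endpoint to Week 16. The bias runs towards no effect. All of this stands, and it limits the weight of the point.

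Several stronger readings are tempting, and the documents do not support them:

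- *The full 14% applies to itch, pain and PGI-S-AD.* Only the ADSS is certain. The time of diary entry is not given, and the 24-hour worst may fall after the dose.
- *A 4-entry floor caps the dilution at 25%.* No floor is stated for Weeks 1 to 14 or 53 to 66.
- *The 4.67-point threshold also applies at Week 53.* In Period 2, 4-point itch response is measured from the originating-study baseline, so it does not carry over. Week 53 is also not a named time point.
- *The size holds for main-study patients at Week 1.* Their change is measured from the originating-study baseline, about 16 treated weeks earlier, so Day 1 need not equal it. The current Table JAHN.6.7 has no Week 0 to 16 diary rows for them.
- *Time to 4-point itch reduction in the first 14 days is biased.* SAP Section 4.3 does not say that this uses the weekly mean.
- *Period 2 always double-counts the visit day.* Overlap arises only if the first Period 2 dose falls after that day.

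It is also fair to say that Days 2 to 7 is not perfectly clean for a 24-hour item: a Day 2 entry made earlier in the day than the Day 1 dose still reaches back before it.

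**Conclusion.** The point holds in limited form. A wholly pre-dose ADSS entry is always placed in the first on-drug week whenever Day 1 is completed. For addendum patients, assuming that entry equals baseline and the effect is steady over Days 2 to 7, the Week 1 mean change is understated by 14% with a full diary and by more with fewer entries. For the 24-hour items, 14% with a full diary is an upper bound set by the unstated entry time.

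The two Period 2 anchors are inconsistent as written. The consequence beyond L = 0 depends on whether the first Period 2 dose follows the visit day. It would dilute the early withdrawal or down-titration contrast; arms that stay on the same dose are little affected.

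The reach is exploratory Week 1 and early Period 2 diary summaries only. A reader should not infer any bias in the Week 16 itch, IGA or EASI results.

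**What to change.** 1. Define Week 1 as Days 2 to 7, leave later weeks unchanged, and do not count the Day 1 ADSS entry as post-baseline.
2. In Period 2, anchor both the Week 52 baseline and the Week 53 to 66 windows on the first Period 2 dose, with Week 53 as Days 2 to 7 from that dose. State that the day counts used as limits for Weeks 67 and 68 follow the same anchor.
3. Apply to Weeks 1 to 14 and 53 to 66 the 4-entry minimum already used for baseline and Weeks 15 and 16.
4. SAP Version 8 records that data to Week 104 are locked, so for those data report the new windows as a labelled sensitivity re-derivation beside the planned summaries.

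The cost is SAP wording and a modest re-derivation. The first week then has at most six entries, so slightly more Week 1 and Week 53 means will be missing. For the ADSS the dilution is removed: under the same assumptions the estimated Week 1 change rises by a factor of 7/6 = 1.17 with a full diary. For the 24-hour items, a Day 2 entry may still cover a few pre-dose hours, and a footnote should say so.
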